6 STUDY POPULATION

6.1 Study Entry Criteria

For purposes of eligibility, the following definitions apply:

- A woman is considered of childbearing potential (WOCBP), i.e. fertile, following menarche and until becoming post-menopausal unless permanently sterile. Permanent sterilisation methods include hysterectomy, bilateral salpingectomy and bilateral oophorectomy.
- A postmenopausal state is defined as no menses for 12 months without an alternative medical cause. A high follicle stimulating hormone (FSH) level in the postmenopausal range may be used to confirm a post-menopausal state in women not using hormonal contraception or hormonal replacement therapy. However, in the absence of 12 months of amenorrhoea, a single FSH measurement is insufficient.
- A man is considered fertile after puberty unless permanently sterile by bilateral orchidectomy.
- Abstinence is defined as refraining from heterosexual intercourse. True abstinence, when this is in line with the preferred and usual lifestyle of the subject is permitted. Periodic abstinence (e.g., calendar, ovulation, symptothermal, post-ovulation methods), declaration of abstinence for the duration of exposure to IP, and withdrawal are not acceptable methods of contraception.

6.1.1 Inclusion Criteria

Patients must meet all of the applicable criteria to be eligible for enrollment in this study:

1. Age \geq 18 years.
2. Diagnosis of Essential Thrombocythemia per World Health Organization (WHO) diagnostic criteria for myeloproliferative neoplasms ([Arber et al., 2016](#)).
3. Patients who have failed at least one standard therapy (failure is the equivalent of inadequate response or intolerance). European Leukemia Net (ELN) criteria for intolerance / resistance to hydroxyurea (Appendix 16.8) may be used in association with Investigator discretion. Ruxolitinib refractoriness or intolerance will be left to the discretion of the Investigator.
4. Requires treatment in order to lower platelet counts based on patient age over 60 or history of thrombosis.
5. Platelet count $>$ 450 k/ μ L (450×10^9 /L) pre-dose Day 1.
6. Peripheral blast count $<$ 1% pre-dose Day 1.
7. ANC \geq 0.5 $\times 10^9$ /L pre-dose Day 1.
8. Fibrosis Score $<$ grade 2, as per a slightly modified version ([Arber et al., 2016](#)) of the European Consensus Criteria for Grading Myelofibrosis ([Thiele et al., 2005](#)).

9. Life expectancy > 36 weeks.
10. Able to swallow capsules.
11. Amenable to bone marrow evaluations and peripheral blood sampling during the study.
12. Must have discontinued ET therapy at least 1 week (4 weeks for interferon) prior to study drug initiation.
13. Women of childbearing potential (WOCBP) and fertile men (see Section 6.1.) must agree to use an approved method of contraception from Screening until 14 days* after last IMG-7289 dose. Methods of contraception include: estrogen and progestogen combined hormonal contraception which inhibits ovulation; progestogen-only hormonal contraception associated with inhibition of ovulation; intrauterine device (IUD); bilateral tubal occlusion; vasectomized partner in a monogamous sexual relationship (vasectomy or tubal ligation at least six months prior to dosing); and, complete sexual abstinence (defined in Section 6.1). Males with a pregnant partner must agree to use a condom to avoid exposure to the developing child. Patients practicing abstinence must agree to use an approved method of contraception should they become sexually active during the study.

*The risk of embryofetal toxicity is fully mitigated by 28 days which is >10 half-lives of the drug at the doses used in this study.

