5 INVESTIGATIONAL PLAN

5.1 Overview

This is a Phase 2 multi-center, open-label study evaluating the safety, efficacy and pharmacodynamics of IMG-7289 administered orally once daily in patients with essential thrombocythemia (ET).

The therapeutic goal for the treatment of ET is to inhibit the activity of LSD1 in hematopoietic cells for only a fraction of the 24-hour dosing cycle, sufficient to reduce the production of platelets, whose over-production characterizes this condition. Considerations leading to the choice of a safe starting dose include chronic toxicology studies in conjunction with the clinical experience of the patients who have received IMG-7289 to date. Using all of the information available in conjunction with the therapeutic goal for the treatment of ET, an IMG-7289 starting dose of 0.6 mg/kg QD has been selected. Refer to Section 3.6 for additional detail on the rationale for the starting dose and dose regimen.

To ensure patient safety, a Safety Advisory Board (SAB) will perform reviews at least quarterly of safety parameters and pharmacodynamic markers to draw conclusions around the safety and pharmacodynamic effect of IMG-7289. The SAB will also review patient dose titrations and may recommend adjustments.

This study consists of two treatment periods: The Initial Treatment Period (ITP), followed by the Additional Treatment Period (ATP). In the ITP, patients will be treated daily for 169 days. In the ATP, which is iterative, treatment may continue for an additional 169 days in those patients deriving clinical benefit (defined as not meeting “progressive disease” criteria as per Appendix 16.5) and safely tolerating IMG-7289; this definition applies throughout the document and will not be repeated with each reference to clinical benefit), as determined by the Principal Investigator.

All patients will undergo follow-up period visits, including an End-of-Treatment (EoT) visit on the day of last dose or as soon as possible thereafter, a pre-End-of-Study (EoS) visit approximately 7 days post last dose, and an End-of-Study (EoS) visit approximately 14 days post last dose. Patients that do not enter the ATP, or discontinue early, will undergo follow-up beginning with an EoT visit.

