 - Aspartate transaminase (AST) or alanine aminotransferase (ALT) ≥ 2 x the local upper limit of normal
12. Current use of a prohibited medication (e.g., romiplostim) or expected to require any of these medications during treatment with the investigational drug.
13. Known immediate or delayed hypersensitivity reaction or idiosyncrasy to drugs chemically related to IMG-7289 or LSD1 inhibitors (i.e., monoamine oxidase inhibitors; MAOIs) that contraindicates their participation.
14. History of any illness/impairment of gastrointestinal (GI) function that might interfere with drug absorption (e.g., chronic diarrhea), confound the study results or pose an additional risk to the patient by participation in the study; patients with gastric bypass surgery.
15. Use of an investigational agent within less than 14 days, or the equivalent of at least 7 half-lives of that agent, whichever is the longer, prior to the study Day 1.
16. Females who are pregnant or breastfeeding or plan to become pregnant or breastfeed during the study.
17. A concurrent second active and non-stable malignancy (patients with a concurrent second active but stable malignancy, such as non-melanoma skin cancers, are eligible).

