11.1 Pregnancy

It is not known whether IMG-7289 can affect reproductive capacity, and the direct effects of IMG-7289 and the indirect effects of prior IMG-7289 exposure on fetal development are also unknown.

Every effort should be made to prevent pregnancy throughout the entire duration of participation in this study. All patients of reproductive potential involved in the study are required to use effective methods of contraception during the study and for 14 days after the last IMG-7289 dose. Female patients will be instructed to notify the Investigator immediately if they become pregnant; male patients will be instructed to notify the Investigator immediately if they discover that their sexual partner is pregnant. Pregnancy data during the study will be reported in an expedited manner using the Pregnancy Report Form and following the SAE reporting process (see Section 11.2.4). It will be necessary to collect detailed information on the course of any pregnancy occurring in a patient on study, including pregnancies in the partners of male patients, assuming consent to do so is provided. If the outcome and/or a complication of the pregnancy meets serious criteria (i.e., miscarriage or congenital anomaly/birth defect), then it should be reported as an SAE using the SAE Report Form.

Pregnant patients will discontinue study medication for the duration of the pregnancy. The pregnancy will be followed by the Investigator and the outcome of the pregnancy will be reported to the Pharmacovigilance group as per the Study Reference Manual (SRM).

All patients will be encouraged to discuss contraception and pregnancy concerns with their physician in advance of becoming pregnant. Full disclosure of a patient's participation in this study to their general practitioner is strongly recommended.

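### Contraception is required for 14 days after the last dose, but the footnote attached to that figure gives a rationale only for 28 days

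*Protocol*

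**What the plan says.** Criterion 13 in protocol Section 6.1.1, repeated in the synopsis, says that women of childbearing potential and fertile men "must agree to use an approved method of contraception from Screening until 14 days* after last IMG-7289 dose". In both places the asterisk on the 14-day figure leads to this footnote: "The risk of embryofetal toxicity is fully mitigated by 28 days which is >10 half-lives of the drug" at the study doses.

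Section 11.1 states the rule a third time. Patients of reproductive potential are "required to use effective methods of contraception during the study and for 14 days after the last IMG-7289 dose", with no reason given for the length. The same section says that direct effects on the fetus are unknown and that "the indirect effects of prior IMG-7289 exposure on fetal development are also unknown".

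Section 5.1 places the End-of-Study visit about 14 days after the last dose. The synopsis schedules the last serum pregnancy test at that visit.

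**The concern.** A footnote attached to a number should justify that number. This one justifies a number twice as large. An investigator or ethics committee reading the criterion cannot tell whether 14 days is a considered choice with the wrong footnote, or whether 28 days was intended and the rule itself is wrong.

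This is a patient-safety rule in force, in a setting where the protocol says fetal effects are unknown. Section 3.2 adds that loss of the drug's target is lethal to early embryos. That concerns the target and is not a measured toxicity of IMG-7289, but it is a reason to have the period right.

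Women of childbearing potential are likely to be few, because criterion 4 requires age over 60 or a history of thrombosis, but younger women with prior thrombosis can enter. Nearly all male patients are covered, because Section 6.1 counts a man as fertile unless he has had bilateral orchidectomy. How many have a partner who could conceive is not known.

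**Working it through.** **Inputs.** Required period: 14 days (synopsis, 6.1.1, 11.1). Period in the footnote: 28 days, stated to exceed 10 half-lives (synopsis, 6.1.1). The visible text gives no half-life, so the footnote's own claim cannot be reproduced. What can be worked out is what it implies at day 14.

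**Formula.** Fraction of drug remaining at time t = 2^(−t / half-life).

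**What the footnote guarantees.**
- Half-life bound: below 28 / 10 = 2.8 days (67.2 hours).
- At day 28: more than 10 half-lives; remaining below 2^(−10) = 0.098%.
- At day 14: more than 14 / 2.8 = 5 half-lives; remaining below 2^(−5) = 3.1%.

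**Range over assumed half-lives.** All the half-lives below are assumptions; 2.8 days is the footnote's limit. The last column assumes a simple one-compartment model.

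| Half-life (days) | Half-lives in 14 days | Remaining at day 14 | Remaining 24 h after peak |
|---|---|---|---|
| 0.5 | 28 | below 0.001% | 25% |
| 1.0 | 14 | 0.006% | 50% |
| 1.4 | 10 | 0.098% | 61% |
| 2.0 | 7 | 0.78% | 71% |
| 2.8 | 5 | 3.1% | 78% |

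**Thresholds.** Fourteen days reaches the footnote's 10 half-lives only if the half-life is at most 14 / 10 = 1.4 days. The only washout the visible protocol writes in half-lives is exclusion 15, for earlier investigational agents: 14 days "or the equivalent of at least 7 half-lives of that agent, whichever is the longer". That rule has another purpose. Used only as a reference point, 7 half-lives fit into 14 days if the half-life is at most 14 / 7 = 2.0 days.

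**Which rows are plausible.** Section 5.1 states the aim as to "inhibit the activity of LSD1 in hematopoietic cells for only a fraction of the 24-hour dosing cycle" on once-daily dosing, and Section 3.5 describes recovery of platelet production as early as 24 to 48 hours as drug clears. Half-lives of 1.4 to 2.8 days would leave 61% to 78% of the peak when the next dose is due. Part-day inhibition therefore fits the shorter values better, though this is not proof.

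**The case against.** The strongest reply is that the rule is the same in all three places, so nobody receives conflicting instructions, and that the footnote states an upper bound. Risk gone by 28 days may well be gone by 14, and more than 10 half-lives may mean many more. On that reading the footnote is silent on 14 days and does not contradict it. This is correct, and it is why the mismatch does not show that 14 days is inadequate. It does not rescue the footnote, whose only function is to support the figure it is attached to.

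A second reply is that the half-life, or a reason for 14 days, may sit in redacted text or in the Investigator's Brochure. That is fair, and the absence of either is not held against the plan. The mismatch is between a visible sentence and its visible footnote, both intact and current.

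Third, the pharmacology favours a short half-life. With an irreversible inhibitor one would expect the effect to outlast the drug, so recovery within 24 to 48 hours suggests rapid clearance. This stands and limits the practical risk.

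Fourth, other safeguards exist. Section 11.1 says that "Female patients will be instructed to notify the Investigator immediately if they become pregnant" and that "male patients will be instructed to notify the Investigator immediately if they discover that their sexual partner is pregnant", and Section 11.2.3 keeps suspected drug-related serious events reportable after the study. These help less than they first appear to. The notification instruction carries no stated end date, but Section 11.1 otherwise speaks of pregnancies during the study, and the last study visit falls at about day 14.

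**Conclusion.** The concern holds as an internal inconsistency in a safety rule. The required period is half of the only period the protocol describes as fully protective. The stated rationale guarantees more than 5 half-lives at day 14 (under 3.1% remaining), against more than 10 (under 0.1%) at day 28.

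The mismatch itself is certain. Whether 14 days is long enough depends on a half-life that is not visible and on the threshold chosen: it meets 10 half-lives up to 1.4 days and 7 half-lives up to 2.0 days. The documents do not show which figure is wrong. The point should be fixed because some correction is needed whichever figure is right. It has no bearing on sample size, alpha, power or any planned analysis.

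**What to change.** The sponsor holds the pharmacokinetic data and can settle this directly.

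- **If the data support 14 days:** keep 14 days, rewrite the footnote in the synopsis and Section 6.1.1 so that it justifies 14 days, and state the half-life. The cost is one footnote in two places.
- **If they do not:** set the period to 28 days in the synopsis, Section 6.1.1 and Section 11.1, and in the consent form if it states the shorter period (the consent pages were not available for this review). Clarify in Section 11.1 that pregnancy reporting covers the same period.

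The second option costs two more weeks of contraception for women of childbearing potential and fertile men. Its drawback is that the period would run past the End-of-Study visit and its last pregnancy test, both at about day 14. No extra visit or test is needed.

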6.1.2 Exclusion Criteria

Patients will be excluded from the study if they meet any of the following criteria:

1. Hemoglobin < 10 g/dL prior to dosing on Day 1.
2. Transfusion dependency, defined as requiring 2 or more units of pack red blood cells per month for more than 3 months, or a hemoglobin level of ≤ 8 g/dL in the preceding 8 weeks before the start of dosing.
3. Eastern Cooperative Oncology Group (ECOG) questionnaire score of 3 or greater at Screening.
4. History of splenectomy.
5. Has undergone major surgery ≤ 4 weeks prior to starting study drug or has not recovered from side effects of such surgery.
6. Unresolved treatment related toxicities from prior therapies (unless resolved to \leq Grade 1).
7. Uncontrolled active infection.
8. Known positive for HIV if not well-controlled (i.e., undetectable viral load) or infectious hepatitis, type A, B or C.

Note for Italy: Active infection with hepatitis A virus, B virus (positive hepatitis B surface antigen; **note:** positive hepatitis B surface antibody and positive hepatitis B core antibody are not exclusionary provided disease is not active, which should be clearly documented in the patient's medical history) or C virus (patients with positive hepatitis C antibody result would require confirmation of active disease with a positive hepatitis C polymerase chain reaction (PCR) test), seropositivity for human immunodeficiency virus (HIV).

9. Current use of monoamine oxidase A and B inhibitors (MAOIs).

10. Evidence at the time of screening of increased risk of bleeding, including any of the following:
 - Activated partial thromboplastin time (aPTT) > 1.3 x the upper limit of normal
 - International normalized ratio (INR) >1.3 x the local upper limit of normal
 - History of severe thrombocytopenia or platelet dysfunction unrelated to a myeloproliferative disorder or its treatment
 - Known bleeding disorder (e.g., dysfibrinogenaemia, factor IX deficiency, hemophilia, Von Willebrand's disorder, Disseminated Intravascular Coagulation [DIC], fibrinogen deficiency, or other clotting factor deficiency).
11. Evidence at the time of Screening of significant renal or hepatic insufficiency (unless due to hemolysis, or leukemic infiltration) as defined by any of the following local lab parameters:
 - Calculated glomerular filtration rate (GFR; using the Cockcroft-Gault equation) <40 mL/min or serum creatinine > 1.5 x the local upper limit of normal

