9.2.1 Screening (Days -28 to Day -1)

- Review of all Inclusion and Exclusion Criteria
- Complete medical/medication history including:
 - 2016 WHO criteria for ET (Appendix 16.2).
 - Disease history (i.e., past bleeding episodes and thromboembolic events)
 - History of all treatments for their current disease (including clinical course with hydroxyurea and/or other ET therapy) or any previous oncologic conditions; including chemical, surgical and/or radiotherapeutic
 - All concomitant medication, in addition to any used in the 15 days prior to Screening
- Calculate ECOG Performance Status (Appendix 16.4)
- MPN-SAF, to be completed as close to Day -7 as possible. Additionally, provide patient with copy of the MPN-SAF for completion prior to dosing on Day 1. (Appendix 16.6)
- Full PE, including Vital Signs – review of all body systems as indicated by signs/symptoms
- Height (without shoes)
- Full Local Laboratory Assessment
- Coagulation
- Urinalysis
- **Note:** In Italy, HIV, HAV, HBsAg, HBsAb, HBcAb and HCV testing must also be performed.

CCI

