12.4 Study Endpoints

12.4.1 Primary Endpoints

- The safety and tolerability of IMG-7289 will be assessed by the analysis of adverse events (AEs), as well as changes in physical examinations, vital signs and laboratory values as detailed below.
 - Monitoring of Adverse Events (AEs) including determination of thromboembolic events, dose limiting toxicities (DLTs), serious adverse events (SAEs), and AEs. AEs will be assessed CCI [REDACTED]
[REDACTED], using the National Cancer Institute Common Terminology Criteria for Adverse Events (NCI CTCAE), Version 5.
 - Changes in physical examinations, vital signs and laboratory values will also be evaluated CCI [REDACTED]
- The reduction of platelet counts will be evaluated and assessed based on local laboratory measurements of platelet counts from Day 1 to each visit where platelets are measured.

CCI [REDACTED]

Demographics will be tabulated and summarized. Medical and surgical history data at Screening will be listed, as will Physical Examination data [redacted] at Screening, and at subsequent visits. All characteristics at baseline [redacted]

[redacted] will be tabulated and summarized.

All patients receiving at least one dose of IMG-7289 will be included in the safety analysis.

Laboratory values outside the laboratory normal ranges will be summarized and assessed [redacted]

Treatment-emergent adverse events will be coded using the Medical Dictionary for Regulatory Activities (MedDRA) and summarized [CCI]

Concomitant medications will be listed by patient and coded using the WHO drug dictionary. Medical history will be listed by patient.

Descriptive statistics [CCI] will be calculated for quantitative safety data as well as for the differences to baseline, when appropriate. [CCI]

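### Inclusion 13 accepts combined estrogen-progestogen contraception with no thrombosis-related condition, although inclusion 4 in practice admits women of childbearing potential only with a prior thrombosis

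*Protocol*

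**What the plan says.** Inclusion 13 in Protocol Section 6.1.1 applies to women of childbearing potential and to fertile men. It requires an approved contraceptive method from Screening until 14 days after the last dose, and the first method it lists is "estrogen and progestogen combined hormonal contraception which inhibits ovulation". The synopsis carries the same entry. Criterion 13 is unredacted in both places.

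Inclusion 4 in the same section reads "Requires treatment in order to lower platelet counts based on patient age over 60 or history of thrombosis". All applicable inclusion criteria must be met.

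Section 6.1 defines a woman as being of childbearing potential "following menarche and until becoming post-menopausal unless permanently sterile", and defines the postmenopausal state as 12 months without menses and without another medical cause.

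Criterion 13 already contains a condition that applies to one sex only: "Males with a pregnant partner must agree to use a condom to avoid exposure to the developing child".

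**The concern.** Read separately, each criterion is unremarkable. Read together, inclusion 4 effectively selects women of childbearing potential for a previous thrombosis, and inclusion 13 then offers that group an estrogen-containing method with no condition tied to thrombosis. Protocol Section 3.1 itself describes ET as carrying a raised rate of thrombosis.

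What is at stake is the safety of individual patients. A site that follows the criterion exactly may enrol a woman with ET and a prior thrombosis on a combined method and record her as compliant with the contraception requirement.

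**Working it through.** No arithmetic on alpha, power or event rates applies. The check is to read the criteria side by side.

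**Step 1: routes through inclusion 4.** The criterion is (age over 60) OR (history of thrombosis). For a woman aged 60 or under the first branch is false, so the second must be true.

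**Step 2: who is of childbearing potential.** Under Section 6.1 the status ends at menopause or permanent sterilisation. In practice such a woman is 60 or younger, so step 1 leaves only the thrombosis route. The text does not strictly bar a woman over 60 who is neither postmenopausal nor sterilised, which is why the conclusion is stated as holding in practice.

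**Step 3: what inclusion 13 asks of her.** Six methods are listed: combined hormonal, progestogen-only hormonal, intrauterine device, bilateral tubal occlusion, vasectomized partner, and abstinence. Any one suffices. The combined entry is qualified only by inhibition of ovulation, which bears on contraceptive efficacy and not on thrombotic risk.

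**Step 4: whether other visible text restricts the method.**

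| Place in the protocol | What it covers | Limits combined contraception after thrombosis? |
|---|---|---|
| 6.1.2, exclusion 10 | "Evidence at the time of screening of increased risk of bleeding, including any of the following" | No; bleeding risk only |
| 6.1.2, exclusion 12 | Prohibited medications, with one example | Not in visible text |
| 6.5 | Supportive care, CYP interactions, platelet rebound after stopping | No |
| 6.6, visible items | Cytotoxic agents and ET therapies, growth factors, MAO inhibitors, anticoagulants and NSAIDs at low platelet counts | No |
| 9.2.1 | "Disease history (i.e., past bleeding episodes and thromboembolic events", plus concomitant medication | Recorded, but not linked to contraceptive choice |
| 11.1 | Effective contraception; "All patients will be encouraged to discuss contraception and pregnancy concerns with their physician in advance of becoming pregnant" | No condition set |
| 12.4.1 | "Monitoring of Adverse Events (AEs) including determination of thromboembolic events" | Detects events; does not restrict entry |

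**Step 5: extent of the change.** One of the six methods would be qualified, and 6 − 1 = 5 would stay unchanged. The entry occurs in 2 places, Section 6.1.1 and the synopsis.

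**The case against.** The strongest objection is that criterion 13 defines what counts as preventing pregnancy and prescribes nothing. A woman may use any listed method, and choosing a safe one is ordinary clinical care. The protocol gives the physician the means: thrombosis history and medications are taken at Screening, patients are encouraged to discuss contraception, and the investigator may withdraw a patient in her best interest (Section 6.3). This largely stands as a reason to rate the point low, since many physicians would avoid the method anyway. It does not remove the gap, because none of those steps conditions the entry requirement.

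Second, the list also serves fertile male patients, whose partners need not have ET. That is correct, and it is why the entry should be qualified and not deleted.

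Third, the documents nowhere say that estrogen raises thrombotic risk. That is true. The link is taken as basic medical knowledge; no outside figure or source is used.

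Fourth, blocks of the protocol are redacted, including text after Section 6.6. A restriction there can be neither confirmed nor ruled out, so the finding is that none is visible.

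A reader might also infer more than the text supports:
- That the method is accepted with no condition at all. It carries the ovulation qualifier; what is missing is a thrombosis-related one.
- That the protocol puts women on estrogen. It is one option of six.
- That the primary endpoint is compromised because it requires the absence of new thromboembolic events. The documents give no number of affected women and no event rate from which such an effect could be shown.

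**Conclusion.** The point holds as a cheap improvement for patient safety. On the visible text, a female patient with a prior thrombosis who uses combined hormonal contraception meets inclusion 13, and in practice a prior thrombosis is the only route by which a woman of childbearing potential enrols.

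The size in patients cannot be derived and may be zero. Nothing is claimed about the primary analysis.

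The conclusion rests on three assumptions: that women of childbearing potential are in practice 60 or younger, that the general medical understanding of estrogen and thrombosis applies here, and that no redacted passage already contains the restriction. Given the last of these, confidence is medium.

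**What to change.** In Section 6.1.1 criterion 13 and in the synopsis, add to the combined-method entry: *not acceptable for female patients with a history of thrombosis; acceptable for female partners of male patients*. Leave the other five methods unchanged. The sponsor's clinicians should confirm the wording. Excluding the method for all female patients would have almost the same effect, since nearly every enrolled woman of childbearing potential would have a prior thrombosis; naming the history keeps the reason visible. If a restriction already exists in redacted text, a cross-reference from criterion 13 would be enough.

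The cost is one phrase in two places, with no new data or procedure. Under Section 14.1 it is still a protocol change that needs written ethics approval before use, across approximately 25 sites in six named countries, so it should travel with the next amendment. The downside for patients is that a woman established on a combined method must change to another listed method before entry.
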